8.5 Demographic and Other Baseline Characteristics

All Baseline summaries will be done on the ITT, PP, and Safety populations by treatment group and overall.

Sex, race, ethnicity, and Baseline IGA will be summarized by counts and percentages. Age, height (cm), weight (kg), body mass index (BMI), and Baseline lesion counts will be summarized with descriptive statistics.

Age, height, weight, BMI, and Baseline lesion counts will be compared among the two treatment groups using a two-way analysis of variance (ANOVA) with factors of treatment group and analysis center. Ethnicity, race, sex, and Baseline IGA will be analyzed with a Cochran-Mantel-Haenszel test stratified by analysis center.

Age will be calculated as the difference in days between the date of birth and the date of informed consent and converted to years by dividing the number of days by 365.25 and using a floor function to drop the decimal portion. In case the exact birth day is missing, day 15 will be used. The BMI will be calculated as weight (kg) divided by squared height (m²).

Medical histories will be coded using the Medical Dictionary for Regulatory Activities (MedDRA) dictionary and presented in a by-subject listing.

The medical history data will be summarized with frequencies and percentages of patients with at least one medical history term reported, and patient frequencies and percentages on the System Organ Class (SOC) and Preferred Term (PT) levels. The number of events will also be summarized. The table will be sorted by overall descending frequency of SOC and then, within a SOC, by overall descending frequency of PT.

8.6 Prior and Concomitant Medications

Concomitant medications will be coded to preferred name and Anatomical Therapeutic Chemical (ATC) classification of ingredients using the World Health Organization (WHO) Drug Global Dictionary, Format B3, Version March 1, 2018.

Medications which start prior to first application will be considered prior medications. Ongoing medications and medications ending after the date of first application will be considered concomitant medications. If the date of first application is unknown and the medication is not

listed as ongoing the interval will be considered “unknown”. If the date of first application is unknown and the medication is listed as ongoing the interval will be considered concomitant.

Incomplete medication start and end dates will be imputed as described in Section 8.1.5.4

A summary of prior and concomitant medications will be provided.

A by-subject listing of all prior and concomitant medications will be presented for the Safety population.

8.7 Analysis of Efficacy

Inflammatory and non-inflammatory lesion counts will be summarized at each evaluation from Baseline through Week 12. Absolute and percent change in lesion counts will be summarized at Weeks 2, 4, 8, and 12. IGA scores will be summarized from Baseline through Week 12 using descriptive statistics. The dichotomized IGA scores will be summarized at Weeks 2, 4, 8, and 12 using descriptive statistics.

Primary, secondary, and supportive efficacy analyses will be conducted on the ITT (primary) population. Primary and secondary efficacy analyses will be conducted on the PP (supportive) population.

All efficacy results will be presented in by-subject listings.

8.7.1 Primary Efficacy Analysis

The primary efficacy analysis will be presented on both the ITT and PP populations.

8.7.1.1 Lesion Counts

Tests of superiority for the absolute change from Baseline in inflammatory and non-inflammatory lesions will be based on either parametric or non-parametric methods consistent with the statistical assumptions required to support the analyses. Specifically, the tests of superiority will be based on an ANCOVA with factors of treatment and analysis center and the respective Baseline lesion count as a covariate or on ranked data submitted to an ANCOVA with factors of treatment and analysis center and the respective Baseline lesion count as a covariate. If the treatment-by-analysis center interaction effect is significant at an alpha less than 0.10, then the effect will be included in the model; otherwise it will be removed.

A skewness test, based on the methods presented by J.H. Zar [4], will be applied to the residuals resulting from an ANCOVA. A two-sided p-value for the skewness test significant at 0.01 will

imply the use of the non-parametric method. If a parametric analysis is indicated, the results of the parametric analysis will be considered the primary analysis. Should a non-parametric analysis be indicated, the absolute or percent changes in lesion counts will be rank transformed prior to submitting them to the ANCOVA. Results of the rank-transformed analyses then will be considered the primary analysis; however, results of the non-ranked transformed analyses will also be presented.

The following steps provide a brief synopsis of the process that will be followed.

1. Missing data will be imputed using multiple imputation. Refer to Section 8.1.5.1.
2. The pooling analysis will be conducted. Refer to Section 8.1.7.
 - a. The treatment-by-analysis center interaction p-values from both parametric and non-parametric (unranked and ranked) analyses will be presented, along with the skewness p-value calculated from the residuals from the unranked ANCOVA. The skewness p-value will determine which analysis results to report:
 - i. Skewness p-value > 0.01 : Report results based on the parametric (unranked) approach.
 - ii. Skewness p-value ≤ 0.01 : Report results based on the non-parametric (ranked) approach.
3. For the primary efficacy analysis
 - a. Results of both parametric and non-parametric (unranked and ranked) analyses will be presented. For each, data will be submitted to an ANCOVA with factors of treatment and analysis center and Baseline lesion count as a covariate (if the treatment-by-analysis center interaction p-value is ≤ 0.10 , the interaction will also be included in the model). The residuals from the unranked analysis will be used to calculate the skewness p-value. The skewness p-value will determine which analysis results to report:
 - i. Skewness p-value > 0.01 : Report results from the parametric (unranked) ANCOVA.
 - ii. Skewness p-value ≤ 0.01 : Report results from the non-parametric (ranked) ANCOVA.
4. If there was a significant treatment by analysis center interaction (as determined in step 1 – the pooling analysis), a sensitivity analysis will be performed as described in

Section 8.1.7 to find the extreme analysis center(s). Then step 3 above will be repeated the extreme analysis center(s) removed, to confirm the treatment response.

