8. STATISTICAL AND ANALYTICAL PLANS

8.1 General Methodology

All statistical processing will be performed using SAS® version 9.3 or later unless otherwise stated. Statistical significance will be based on two-tailed tests of the null hypothesis resulting in p-values of 0.05 or less.

The primary method of handling missing efficacy data will be based on estimation using the method of Markov Chain Monte Carlo (MCMC) imputation. The estimation will be done for each treatment group separately so that the pattern of missingness for one group does not influence the estimation of missing data for another group. Groups of complete datasets following the estimation will be concatenated to form analysis datasets for the comparative

analyses and subsequent imputation result inference with SAS PROC MIANALYZE. Descriptive statistics will also be derived from the multiply imputed datasets.

Sensitivity analyses for the primary efficacy endpoints will use 3 methods. For the lesion count endpoint, the first method will use a repeated measures analysis of covariance (ANCOVA), with treatment, analysis center, visit (i.e., Week 2, Week 4 and Week 8), and treatment group by visit interaction as independent factors and a covariate of Baseline. In this analysis, data from all post-baseline visits will be included with no imputation for missing data.

The second sensitivity analyses will use the model based multiple imputation method to impute missing data for the absolute change at Week 12.

The third sensitivity analysis will involve a tipping point analysis.

Similar methods for the dichotomized IGA will involve a repeated measures logistic regression model and a model based multiple imputation and tipping point analysis.

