8.7.1.2 Investigator Global Assessment (IGA)

The IGA will be dichotomized into “success” and “failure” with a patient considered a success for those visits if the IGA is at least 2 grades less than Baseline and “Clear” or “Almost Clear”. The analysis of the dichotomized IGA will be based on a logistic regression test with factors of treatment group and analysis center.

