9. DETERMINATION OF SAMPLE SIZE

The following power calculations are based on the observed Week 12 results of the Phase 2 study, SGT-65-02. This study was a six-arm trial including S6G5T-3 and Vehicle Cream in the treatment of acne vulgaris. Estimates from the S6G5T-3 arm were used in the power assessments. The anticipated randomization ratio is 2:1 for S6G5T-3 and S6G5T-8 Vehicle Cream, respectively. The computations were performed with nQuery Advisor Version 7.0 using a two-sided test with a statistical significance value of 0.05.

A sample size of 274 in the S6G5T-3 and 137 in the Vehicle Cream group (total of 411) has 99% power to detect a statistically significant difference in inflammatory lesions. The estimated absolute change from Baseline in treatment means were -16.7 and -12.2 for S6G5T-3 and Vehicle Cream, respectively, with a common standard deviation of 10.0.

A sample size of 146 in the S6G5T-3 and 73 in the Vehicle Cream group (total of 219) has 99% power to detect a statistically significant difference in non-inflammatory lesions. The estimated absolute change from Baseline in treatment means were -23.7 and -13.7 for S6G5T-3 and Vehicle Cream, respectively, with a common standard deviation of 19.0.

A sample size of 231 in the S6G5T-3 and 116 in the Vehicle Cream has group (total of 346) has 99% power to detect a statistically significant difference the proportion of Patients who have at least a 2-grade reduction at Week 12 from Baseline in IGA and are Clear or Almost Clear. The estimated percentages with a 2-grade reduction at Week 12 from Baseline in the IGA and Clear or Almost Clear are 33.3% and 12.6% for S6G5T-3 and Vehicle Cream, respectively.

Therefore, a total of 420 Patients has adequate power to demonstrate statistical significance of S6GT5-3 over S6GT5-8 Vehicle Cream for the lesion count endpoints as well as dichotomized IGA.

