(Intent-to-Treat Population)

	E-BPO/E-ATRA 3%/0.1% Cream (N=xxx)	Vehicle Cream (N=xxx)	Skewness P-Value	Treatment P-Value
Inflammatory Lesion Count – Absolute Change from Baseline				
LSMean ^a	xx.x	xx.x	x.xxx ^b	x.xxx ^a
LSSD ^a	xx.xx	xx.xx		x.xxx ^c
Non-Inflammatory Lesion Count – Absolute Change from Baseline				
LSMean ^a	xx.x	xx.x	x.xxx ^b	x.xxx ^a
LSSD ^a	xx.xx	xx.xx		x.xxx ^c
At Least Two Grade Reduction from Baseline and Achieving Clear or Almost Clear				
Success	xx.x%	xx.x%	N/A	x.xxx ^d
Failure	xx.x%	xx.x%		

^a Least squares means, standard deviations and treatment p-value from an analysis of covariance with factors of treatment group and analysis center and the respective Baseline lesion count as a covariate. Negative least squares means values represent decrease from Baseline.

^b Skewness test, based on methods presented by J.H. Zar (1984), assessed for each imputed dataset. The average p-value is presented.

^c P-value from a ranked analysis of covariance with factors of treatment group and analysis center and the respective Baseline lesion count as a covariate.

^d P-value from a logistic regression with factors of treatment group and analysis center.

Note: Multiple imputation (MCMC) used to impute missing values.

SOURCE: USERNAME/SPONSOR/PROJECTJOBNAME (DATE, TIME)

{NOTE TO PROGRAMMER: ADJUST FOOTNOTE “d” IF FIRTH’S PENALIZED LIKELIHOOD IS NEEDED}

Repeat Table 14.2.1.2 for the following table:

Table 14.2.1.3: Primary Efficacy Analysis: Absolute Change from Baseline in Lesion Counts and Dichotomized IGA Success at Week 12 (Per-Protocol Population)

Update footnote to “Note: Missing values imputed using last observation carried forward.”

Table 14.2.2.1.1: Summary of Inflammatory Lesion Counts at Each Evaluation
(Intent-to-Treat Population)
(Page 1 of 4)

Inflammatory Lesion Counts	E-BPO/E-ATRA 3%/0.1% Cream (N=xxx)	Vehicle Cream (N=xxx)
Baseline		
n	xx	xx
Mean	xx.x	xx.x
SD	xx.xx	xx.xx
Median	xx.x	xx.x
Min. to Max.	xx to xx	xx to xx
Week 2		
n	xx	xx
Mean	xx.x	xx.x
SD	xx.xx	xx.xx
Median	xx.x	xx.x
Min. to Max.	xx to xx	xx to xx
Change from Baseline		
n	xx	xx
Mean	xx.x	xx.x
SD	xx.xx	xx.xx
Median	xx.x	xx.x
Min. to Max.	xx to xx	xx to xx
Percent Change from Baseline		
n	xx	xx
Mean	xx.x	xx.x
SD	xx.xx	xx.xx
Median	xx.x	xx.x
Min. to Max.	xx to xx	xx to xx

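### A treatment-by-center pre-test chooses the primary lesion-count model, and the rule is incompletely specified; the cost is an unfixed estimate and some precision, not alpha or power

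*SAP*

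**What the plan says.** SAP 8.7.1.1 defines the primary lesion-count test as an ANCOVA on treatment, analysis center and baseline count, ranked or unranked. It then adds a switch: "If the treatment-by-analysis center interaction effect is significant at an alpha less than 0.10, then the effect will be included in the model". If the interaction does not reach that level, it is taken out. Step 3a of the same section repeats the instruction ("the interaction will also be included in the model"), but with a p-value at or below 0.10 as the trigger. Protocol 17.4.1 and the statistical part of the protocol synopsis carry the sentence as well. SAP 8.7.3 applies the primary lesion-count methods to the percent-change secondaries, so they inherit the rule.

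The shell for the primary results, Table 14.2.1.2, names only the main-effects model. Its footnote for the ranked test reads: "P-value from a ranked analysis of covariance with factors of treatment group and analysis center and the respective Baseline lesion count as a covariate". The footnote for the LS means and the unranked test uses the same terms.

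The IGA co-primary has no switch. SAP 8.7.1.2 specifies a "logistic regression test with factors of treatment group and analysis center".

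SAP 8.1.7 separately tests the interaction at 0.10 for all three primary endpoints. If it is significant, the analysis is repeated without the extreme centers.

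**The concern.** The primary estimate should be fixed before the data are seen. Here a low-power test at the 10% level decides which of two models is primary, and inflammatory and non-inflammatory counts can end up with different models in one trial.

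The two models do not estimate the same quantity unless all centers are the same size or share one treatment effect. Without the interaction, centers count roughly by size. With it, and with the usual software defaults, every center counts equally. SAP 8.1.7 sets a floor of 15 patients per analysis center but no ceiling, and it pools only sites below the floor, so sizes will differ.

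The switch is also not fully specified:

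- The threshold is strict in one place and inclusive in another.
- Five imputed data sets give five interaction tests. Table 14.2.1.1 says that skewness p-values are averaged but gives no rule for the interaction p-value. The general instruction to use PROC MIANALYZE does not say how a test on many degrees of freedom is to be combined.
- Center weights are not stated.

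Two programmers could therefore report different primary p-values from the same data.

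**Working it through.** **Inputs from the documents.** Two-sided 0.05 (SAP 8.1). 2:1 allocation and a planned total of 420, so 280 and 140 (SAP 6.1.2 and Section 9). Inflammatory "treatment means were -16.7 and -12.2 for S6G5T-3 and Vehicle Cream, respectively, with a common standard deviation of 10.0", a difference of 4.5. Non-inflammatory difference 10.0, SD 19.0. Up to 31 sites (SAP) or 25 (protocol). Center minimum 10 active plus 5 vehicle. Five imputations.

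**Assumptions.** Center sizes are not given, so a range is used. Default LS means and Type III tests apply once the interaction is in. Allocation is exactly 2:1 within centers. Data are normal, and no dropout is applied because Section 9 gives no rate.

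**The plan's own figure.** With 274 and 137, SE = 10 × sqrt(1/274 + 1/137) = 1.046. Power = Φ(4.5/1.046 − 1.96) = 99.0%, as stated. (For non-inflammatory lesions the stated 146 and 73 give 95.7% by the same formula, not 99%. That is a separate matter and does not affect 280/140.)

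**Main-effects model at 280/140.** Inflammatory SE = 10 × sqrt(1/280 + 1/140) = 1.035, power 99.2%. Non-inflammatory SE = 19 × sqrt(1/280 + 1/140) = 1.967, power Φ(10/1.967 − 1.96) = 99.9%.

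**Interaction model.** In a center of size n, the treatment difference has variance SD² × (3/(2n) + 3/n) = 4.5 SD²/n. An equally weighted mean over C centers has variance (4.5 SD²/C) × mean(1/n). The size-weighted estimate has variance 4.5 SD²/N. At equal residual SD, therefore:

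SE ratio = sqrt(mean(n) × mean(1/n)), which is at least 1 and equals 1 only if all centers are the same size.

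| Assumed layout (N = 420) | C | mean(n) | mean(1/n) | SE ratio | SE, inflammatory | Power with interaction model |
|---|---|---|---|---|---|---|
| 28 centers of 15 | 28 | 15 | 0.0667 | 1.00 | 1.035 | 99.2% |
| 12 of 15, 8 of 30 | 20 | 21 | 0.0533 | 1.06 | 1.095 | 98.4% |
| 16 of 15, 2 of 30, 2 of 60 | 20 | 21 | 0.0583 | 1.11 | 1.146 | 97.5% |
| 16 of 15, 2 of 90 | 18 | 23.3 | 0.0605 | 1.19 | 1.230 | 95.5% |

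In the last layout, non-inflammatory power is 99.0%.

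**How often the term enters.** With no true interaction, about 10% per endpoint. For at least one of the two, 1 − 0.9² = 19% if independent.

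**What happens on entry (simulated, no true interaction).** Entry selects data sets in which the interaction absorbs more variation than expected, so the residual SD of the larger model is about 2% lower. This takes the closed-form range of 0% to +19% down to about −2% (equal centers) to +17% (two 90-patient centers).

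Sites were also simulated: 25 or 31 of them, with recruitment from fairly even to very uneven, pooled by the SAP rule, 6,000 trials per setting. The median SE change on entry was +1.5% to +9%, and the SE was wider in 92% to 100% of entering trials. The estimate moved by 0.3 to 0.5 lesions on average. It moved by about 0.7 with two 90-patient centers and not at all with equal centers.

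Type I error given entry was 5.7% to 7.8% in the fixed layouts. It was 5.0% to 7.0% in the recruitment settings, each of which rests on only about 600 entering trials.

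**Overall effect.** Overall type I error was 5.0% to 5.2% in the fixed layouts. This fits the arithmetic: 10% entry times an excess of about 2 points adds about 0.2. Overall inflammatory power fell by at most about 0.5 points. The worst row of the table gives 0.10 × (99.2 − 95.5) = 0.37.

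**The case against.** The best defense is that the rule is written down before unblinding, agrees in substance between protocol and SAP, and does little harm. The numbers above bear out the last part: no wrong trial conclusion is shown to become materially more likely. Interaction p-values (Table 14.2.1.1), by-center results (Tables 14.2.2.2, 14.2.3.2 and 14.2.4.2) and the analysis without extreme centers are all planned. This limits the seriousness. It does not answer the missing weights, the two thresholds or the missing combination rule.

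A reader might infer more than the documents support in four ways.

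- **That the plan prescribes equal center weights.** It names no weights, no test type and no LS-means option. Equal weighting is the software default and is assumed here.
- **That the selected model always has the larger SE.** With equal centers it is about 2% smaller.
- **That the primary table contradicts the rule.** It is a mock shell. Programmer notes elsewhere adjust footnotes for other contingencies, but none covers this one. It is better read as a missing footnote variant than as a statement that the term is excluded.
- **That the absence of a switch for IGA is an error.** SAP 8.1.7 tests the IGA interaction at the same level with the same follow-up. The endpoints are treated differently, but that alone is not a mistake.

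**Conclusion.** The point holds in a limited form. A pre-test decides the primary model for two of the three co-primary comparisons, and the rule leaves the threshold, the combination over imputations and the center weights open. Under default weighting, entry (about 10% per endpoint with no true interaction) replaces a size-weighted effect by an equally weighted one. The SE changes by about −2% to +17%, the estimate moves by 0 to 0.7 lesions on average against 4.5, and type I error given entry is about 6% to 8% in the fixed layouts.

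It would be wrong to read this as material alpha inflation or an underpowered trial. Overall type I error stays at about 5%, the overall loss of power is at most about 0.5 points, and even with the interaction in the model every layout tabulated keeps at least 95% power. What is gained is a fixed, reproducible primary estimate and modest precision.

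The sizes rest on assumed center layouts, normal data, no dropout and no true interaction. With a true interaction the term would enter more often, and the choice of weights would matter more.

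**What to change.** Before unblinding:

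- Delete the conditional-inclusion sentence in SAP 8.7.1.1 and the matching parenthesis in step 3a. Delete the same sentence in protocol 17.4.1 and the synopsis.
- State that the main-effects ANCOVA is the only primary lesion-count model.
- Reword SAP 8.1.7, which now places the interaction inside the primary analyses, so that the interaction test and the extreme-center analysis are supportive only. Protocol 17.4.5 has parallel wording.
- List the departure from the protocol in SAP Section 10. The SAP Preface says an amendment will be considered for major differences such as changes to the primary-endpoint analysis, so consider one here.

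The table shells already fit this model. The cost is document wording and possibly an amendment, with no new data or programming of substance.

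The downside is that, if effects truly differ between centers, the primary estimate is a size-weighted average. Center-specific results still appear in the planned by-center tables.

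If the sponsor prefers to keep the switch, the SAP needs a single threshold, stated center weights, a rule for combining the interaction test over the five imputations, and a footnote variant for the primary table.

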8.7.1.2 Investigator Global Assessment (IGA)

The IGA will be dichotomized into “success” and “failure” with a patient considered a success for those visits if the IGA is at least 2 grades less than Baseline and “Clear” or “Almost Clear”. The analysis of the dichotomized IGA will be based on a logistic regression test with factors of treatment group and analysis center.

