12.18 Investigator Global Assessment (IGA)

The Investigator Global Assessment (IGA) will be performed at visits: Screening, Baseline, Weeks 2, 4, 8 and 12/ End of Study or Early Termination.

Patients are eligible for enrollment if they have facial acne with a global severity grade of a 3 (moderate) or a 4 (severe) on the IGA scale at Baseline.

The IGA scale provided in the following Table will be used to describe the global severity grade and subsequent score:

Table 2: Investigator Global Assessment (IGA) Scale

Grade	Description
0 – Clear	Normal, clear skin with no evidence of acne vulgaris
1 – Almost Clear	Rare non-inflammatory lesions present, with rare non-inflamed papules (papules must be resolving and may be hyperpigmented, though not pink-red)
2 – Mild	Some non-inflammatory lesions are present, with few inflammatory lesions (papules/pustules only; no nodulo-cystic lesions)
3 – Moderate	Multiple Non-inflammatory lesions and, inflammatory lesions are evident: several to many comedones and papules/pustules, and there may or may not be one small nodulo-cystic lesion
4 – Severe	Inflammatory lesions are more apparent, many comedones and papules/pustules, there may or may not be a few nodulo-cystic lesions

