17.4.2 Test of Superiority for IGA

The IGA will be dichotomized into “success” and “failure” with a Patient considered a success for those visits if the Investigator’s Global Assessment is at least 2 grades less than Baseline and “Clear” or “Almost Clear”. The analysis of the dichotomized IGA will be based on a logistic regression test with factors of treatment group and analysis center.

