6.1.2 Method of Assigning Subjects to Treatment Groups

It is planned that approximately 420 Patients, who meet the inclusion/exclusion criteria, will be enrolled in this study at up to 31 U.S. study sites. Patients will be at least 9 years of age and older, of either gender.

The study products will be administered in a double-blinded fashion (i.e., the treatment assignment will not be known to the Patient or to study personnel including Sol-Gel and its representatives). Patients will be instructed not to discuss the study product with the study personnel. Patients will be randomly assigned, in a 2:1 ratio, as follows:

- E-BPO/E-ATRA 3%/0.1% Cream (Product S6G5T-3) (280 Patients)
- Vehicle Cream (Product S6G5T-8) (140 Patients)

Each Patient who signs an informed consent, meets inclusion/exclusion criteria, and successfully completes the screening procedures will be enrolled in the study. The Patient randomization schedule will be a permuted block design stratified by investigational site. Blocks will be composed of 3 treatment assignments in a ratio of 2:1 study product and vehicle respectively. Complete blocks from the randomization schedule will be allocated to investigational sites as they randomize Patients. Patients will be randomized through the IWRS and assigned a unique randomization ID assigning treatment group. The study product supplies will be packed in kits containing 4-pumps and will be numbered in a scrambled randomized method. The kits will be dispensed by the IWRS according to the Baseline assigned randomized treatment group.

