8.1.4 Adjustments for Covariates

Baseline lesion count will be a covariate for the primary efficacy endpoint for acne lesion counts. No other covariates are planned to be used in the analyses for this study.

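### The co-primary IGA model leaves out baseline severity, which every patient has recorded; the loss is modest efficiency, not bias, and costs little to recover before unblinding

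*SAP*

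**What the plan says.** SAP 8.7.1.2 defines the test of the IGA co-primary: "The analysis of the dichotomized IGA will be based on a logistic regression test with factors of treatment group and analysis center". SAP 8.1.5.2 step 2 applies the same two factors to each imputed data set. Protocol 17.4.2 agrees: "logistic regression test with factors of treatment group and analysis center".

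SAP 8.1.4 gives the lesion-count endpoints their baseline count as covariate and then closes the list: "No other covariates are planned to be used in the analyses for this study". The IGA repeated-measures and model-based imputation analyses (SAP 8.7.2.2.1 and 8.7.2.2.2) contain no baseline severity term either.

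A patient counts as a "success for those visits if the IGA is at least 2 grades less than Baseline and “Clear” or “Almost Clear". Protocol 12.18 limits entry to grades 3 and 4. Severity plays no part in allocation (SAP 6.1.2): "The Patient randomization schedule will be a permuted block design stratified by investigational site".

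Baseline IGA is used elsewhere: in the imputation of missing IGA values (SAP 8.1.5.2), in a between-arm baseline comparison (8.5) and in descriptive subgroups (8.1.11).

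**The concern.** Two of the three co-primaries adjust for baseline severity and the third does not. A grade-3 patient must fall 2 grades to reach success and a grade-4 patient 3, so baseline grade probably predicts the outcome. Baseline counts probably do too: entry allows 20-100 inflammatory and 30-150 non-inflammatory lesions, while grade 1 tolerates only rare ones.

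Under SAP 8.1.8 all three co-primaries must be significant before any secondary endpoint can count, so efficiency lost on IGA affects the whole testing sequence. And if the baseline comparison in SAP 8.5 showed an excess of severe patients in one arm, no prespecified IGA analysis would account for it. An adjustment chosen at that stage would be post hoc.

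**Working it through.** **Inputs from SAP section 9:** success 33.3% v 12.6%, 2:1 allocation, two-sided 0.05, 99% power from 231 + 116 patients (total given as 346), 420 planned (280 + 140). **Assumed, because the documents are silent:** grade-4 share 5-30%; odds ratio for success, grade 4 v grade 3, 0.20-0.75.

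**1. The plan's own figure.** Two-proportion formula, n = vehicle patients, r = 2, d = 0.207, pooled rate (0.126 + 2 × 0.333)/3 = 0.264:

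- Without continuity correction: n = [1.960 √(1.5 × 0.264 × 0.736) + 2.326 √(0.126 × 0.874 + 0.333 × 0.667/2)]² / 0.207² = 108.1.
- With it: n = (108.1/4) × [1 + √(1 + 6/(108.1 × 2 × 0.207))]² = 115.2 vehicle, 230.5 active, 345.7 in total. Each rounded up gives 116, 231 and 346, so the plan's figures reproduce.

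**2. Unadjusted logistic test at 280 v 140** (center ignored).

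- Log odds ratio = ln(0.333/0.667) − ln(0.126/0.874) = 1.242.
- SE = √[1/(280 × 0.333 × 0.667) + 1/(140 × 0.126 × 0.874)] = 0.2845.
- z = 4.366; power = Φ(4.366 − 1.96) = 99.2%.

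**3. Adding baseline IGA, marginal rates held fixed.** With weights w = n·p(1 − p) per arm and grade, the information on treatment is the sum over grades of w_active × w_vehicle/(w_active + w_vehicle). Worked case, 15% severe and odds ratio 0.33:

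- Grade 3: success 36.4% v 13.9%, weights 55.08 and 14.27, information 11.33.
- Grade 4: success 15.9% v 5.1%, weights 5.61 and 1.01, information 0.86.
- The conditional log odds ratio is 1.262 and its SE is 1/√12.19 = 0.2864, so z = 4.406. The squared statistic rises by (4.406/4.366)² − 1, about 1.8%, or 0.018 × 420 = about 8 patients.

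The SE widened slightly, from 0.2845 to 0.2864. The gain is in the test statistic, not in a narrower odds-ratio interval.

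**4. Over the assumed range:**

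| Severe share, odds ratio | Multiplier of z² | Equivalent patients | Power |
|---|---|---|---|
| 5%, 0.75 | 1.001 | about 0 | 99.2% |
| 15%, 0.33 | 1.018 | about 8 | 99.3% |
| 30%, 0.20 | 1.065 | about 27 | 99.5% |

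**5. Smaller effect, assumed 24% v 12.6%.** Unadjusted z = 0.784/0.2906 = 2.698, power 77.0%. With baseline IGA (10-30% severe, odds ratio 0.20-0.50), z = 2.705 to 2.766 and power is 77.2-79.0%.

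**6. Adding a baseline lesion count.** Simulation with 2,000 trials per setting, 14 assumed centers and an assumed log-odds slope of 0.4 per SD: the multiplier for baseline IGA and count together is about 1.04-1.10. At 24% v 12.6%, simulated power rises by about 1-4 points, at best from 81.7% to 85.6%. The simulated unadjusted power (about 81-83%) is above the 77.0% from the formula, so gains should be read within one method.

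**7. Chance imbalance.** With 15% severe, the SD of the arm difference in severe share is √[0.15 × 0.85 × (1/280 + 1/140)] = 3.7 points. Two SD (7.4 points) times an assumed 20-point lower success rate in severe patients shifts the success difference by about 1.5 points. In the worked case of step 3 the gap is about 20 points on active but only 13.9 − 5.1 = 8.8 on vehicle, so 1.5 is at the upper end for that case.

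**The case against.** The best defence is that the choice is explicit, prespecified and the same in both documents, and that the test is valid. Chance imbalance is already part of its sampling error, and even a 2-SD imbalance moves the estimate by about 1.5 points against a planned difference of 33.3 − 12.6 = 20.7. At the plan's own rates power gains at most 0.3 points. The size of any gain rests on assumed inputs and may be close to nil. All of this stands, and it limits the weight of the point.

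It is also fair that baseline grade is not prognostic by definition. For both entry grades, success is simply a Week 12 IGA of 0 or 1, because the 2-grade condition is then met automatically. That grade-4 patients succeed less often is a reasonable expectation, but the documents do not show it. Nor is baseline IGA unused: it enters the imputation, the baseline comparison and the subgroup tables, so a material imbalance would be seen.

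What the defence does not supply is a reason to leave baseline severity out of the one co-primary model that lacks it, when the data are already collected. Seeing an imbalance in a table is not the same as having a prespecified analysis that handles it.

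One caution on the remedy also stands. Three extra covariates in the Week 2 and Week 4 models, where successes may be few, have not been tested.

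**Conclusion.** The omission is certain from the text. Its consequence is a modest loss of efficiency, with chance imbalance in severity left unadjusted. For baseline IGA alone the gain forgone is about 0.1-6.5% in the squared test statistic (0-27 patients); with a lesion count as well it is roughly 4-10%. These figures depend on the assumed severe share, odds ratio and slope.

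A reader might infer that the IGA comparison is biased or invalid, or that the trial is underpowered for it. The documents support neither. Randomization protects the unadjusted test, and power at 33.3% v 12.6% with 420 patients is about 99% either way. The adjustment matters mainly if the true effect is smaller than planned. It is worth making because it is nearly free, provided it is fixed before unblinding.

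**What to change.** Before unblinding:

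- Add baseline IGA (3 v 4), and preferably the two baseline lesion counts, to the Week 12 co-primary IGA logistic model in SAP 8.7.1.2 and 8.1.5.2 step 2, and amend 8.1.4.
- Align the IGA sensitivity models in SAP 8.7.2.2.1 and 8.7.2.2.2 (the latter says that its imputation and analysis models are identical), the footnotes to Tables 14.2.1.2 and 14.2.6.1, and protocol 17.4.2 with the places that repeat the model (synopsis, 17.4.6.2, 17.4.7.2).
- Report the standardized success-rate difference, and specify how it and its variance are pooled across imputations, because the odds ratio becomes conditional on baseline.
- For the supportive models at Weeks 2 and 4, use baseline IGA only, or Firth's penalized likelihood, if successes are few. The SAP foresees Firth in its programmer notes (for example to Table 14.2.1.2), but Table 14.2.11.1 carries no such note.
- State that the PRE-FACE and PGI-C responder models, which borrow the IGA method (SAP 8.7.3 and 8.7.4), do not automatically inherit these covariates.

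Cost: wording edits and a few model lines, with no new data or visits. SAP section 2 says that a protocol amendment will be considered for changes to the primary-endpoint analysis, so one may be needed.
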